Rationale for the study	In the course of ZOSTER-006 and ZOSTER-022, QoL questionnaires were encoded into the respective trial database only for subjects who developed a suspected HZ episode during the study. This was done to assess the QoL of subjects who developed suspected cases of HZ between the vaccine group and the placebo group. The remaining subjects who did not develop suspected cases of HZ completed the questionnaires; however, these questionnaires were never encoded or analysed as part of ZOSTER-006 and ZOSTER-022. The purpose of this study is to allow for the encoding and analysis of all questionnaires for subjects enrolled in ZOSTER-006 and ZOSTER-022. The aim is to assess the baseline frailty of subjects enrolled in ZOSTER-006 and ZOSTER-022 and to investigate the representativeness of the study population to the general population. Additionally, analysis of efficacy, safety and immunogenicity will be performed by frailty status. The study will also explore if quality of life data and subject characteristics reported by the subjects before the onset of HZ would be predictive of HZ.

This should help confirm previously hypothesized predictive factors such as age, stress or functional status, and also to assess other potential risk factors such as frailty, fatigue or emotional and mental health.

Study design

- A multi-country, observational, retrospective study.
- Study population: All subjects enrolled in ZOSTER-006 and ZOSTER-022.
- Type of study: Data to be analysed in this study have been collected in the ZOSTER-006 (eTrack 110390) and ZOSTER-022 (eTrack 113077) and will be combined for assessment of primary, secondary and tertiary objectives.
- Data collection: QoL questionnaires and the year of birth of subjects enrolled in ZOSTER-006 and ZOSTER-022.
 - QoL questionnaires: The *SF-36* is a multi-purpose health survey with 36 questions. The *EQ-5D* is a questionnaire with 5 questions designed as a generic measure of health status that provides a simple descriptive profile and a single index value. The *EQ-5D* defines health in terms of mobility, self-care, usual activities, pain/discomfort and anxiety/depression.
- Method: Frailty scores for study subjects in ZOSTER-006 and ZOSTER-022 will be calculated by incorporating the subject's medical history and items from the *SF-36* and *EQ-5D* questionnaires.

Discussion of study design

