10.7. Statistical methods

Age in years will be computed as the difference between the date of completion of the QoL questionnaire collected at Month 0 and the date of birth.

As this is an exploratory analysis, no adjustment will be done for multiple comparisons (i.e. a 2-sided significance level of 0.05 will be used).

Spearman correlations coefficients will be presented to display the relationships between pairs of variables. In addition, particularly for the QoL variables, the variance inflation factor and the condition indices for testing multicollinearity will be estimated.

A bootstrap analysis will be carried out to evaluate the robustness of the results with respect to the selection of variables in the final multivariate model.

All analyses will be carried out using SAS Version 9.1.3 or later.

GSK vaccines will be responsible for performing the statistical analysis.

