10.7.6.3. Predictive factors for individuals developing HZ

Only subjects in the placebo vaccination group will be included in the analysis of potential predictive factors. A Cox proportional hazards regression model allowing for time-dependent covariates will be fitted to identify which factors are predictive of developing HZ. The model will include time to HZ as the outcome variable and as potential predictors: demographic and clinical characteristics, *SF-36* variables and *EQ-5D* variables. Subjects who did not develop HZ will be censored at the time of their last study visit. The proportional hazards regression model will be used for both minimally adjusted analyses and multivariate analyses. All factors will initially be examined in an age- and sex-adjusted model with stratification for the clinical trial (i.e. ZOSTER-006 and ZOSTER-022). Factors will be included in the multivariate model if they are associated ($P < 0.05$ using a two-sided test) with HZ in the minimally adjusted model. The multivariate model will also include age and gender with stratification for the clinical trial (i.e. ZOSTER-006 and ZOSTER-022). A step-down (backward) variable selection procedure will be used to fit the final multivariate model. This model will be fitted using the PHREG procedure of the *SAS/STAT* package.

Spearman correlations coefficients will be presented to display the relationships between pairs of variables. In addition, particularly for the quality of life variables, the variance inflation factor and the condition indices for testing multicollinearity will be estimated.

In the analysis, the impact of excluding “suspected but not confirmed cases” of HZ will be explored. Three analyses will be performed whereby it will be assumed that “suspected but not confirmed cases” are (1) “Not in at risk group” (2) “In at risk group” and event=0, (3) “In at risk group” and event=1.

Due to the multiple measurements of the *EQ-5D* and *SF-36* over time, repartition in the HZ positive or HZ negative will be dynamic. Subjects who did not develop a confirmed HZ before one-timepoint (Day 0, Month 14, Month 26 and Month 38) will be considered HZ negative at that timepoint, and the characteristics and QoL scores reported for this subject at the previous timepoint will be considered as **not leading** to HZ.

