Subjects who developed a confirmed HZ during the interval between two timepoints will be considered HZ+ at the later timepoint. Characteristics and QoL scores reported for this subject at the last timepoint before onset of HZ will be considered **leading** to HZ.

Example: A subject developed a confirmed HZ episode on Month 22:

- Subject’s characteristics and QoL scores reported at Day 0 will be considered as **not leading** to HZ.
- Subject’s characteristics and QoL scores reported at Month 14 will be considered as **leading** to HZ.

- Subject's characteristics and QoL scores reported at timepoints posterior to onset of HZ (Month 26 and Month 38) will be censored.

Further, details regarding the analysis will be provided in the statistical analysis plan.

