6.3.4. Predictive factors for subjects developing HZ

A Cox regression model allowing for time-dependent covariates will be fitted to identify which factors are predictive of developing HZ. The model will include time to HZ as the outcome variable, the demographic variables age and gender and the time dependent *SF*-36 variables and *EQ-5D* variables as potential predictors. This analysis will be performed for subjects in the Placebo group in the TVC.

Subjects who did not develop HZ will be censored at the time of their last study visit. The regression model will be used for both minimally adjusted analyses and multivariate analyses. All factors will initially be examined in an age- and gender-adjusted model with further adjustment for the original study (ZOSTER-006 or ZOSTER-022). Factors will be included in the multivariate model if they are associated (P < 0.05 using a two-sided Wald test) with HZ in the minimally adjusted model. The multivariate model will also include age, gender and original study. A step-down (backward) variable selection procedure will be used to fit the final multivariate model. This model will be fitted using the PHREG procedure of the SAS/STAT package.

The parameter estimates and standard error of each SF-36 and EQ-5D parameter from the minimally adjusted model will be presented. The final multivariate model will also be presented.

The analysis will be performed with the event defined as a HZ confirmed case. Three separate analyses will be performed examining the impact of excluding suspected but not confirmed cases.

The first analysis will exclude subjects who had a suspected case that was later proven not to be a HZ episode.

204878 (ZOSTER-064) Statistical Analysis Plan Amendment 1

The second analysis will include all subjects. Those subjects who had a suspected case that was later proven not to be a HZ episode will be censored at their latest available assessment and will be considered not to have had the event.

The third analysis will also include all subjects. The definition of event will be changed to having a suspected case of HZ.

The distribution of confirmed cases of HZ amongst suspected cases will be presented by age group for subjects in the placebo group in the TVC.

Details of the process behind the inclusion of time dependent covariates are included in section 7.4

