7.4. Predictive factors for individuals developing HZ

Only subjects in the placebo group will be included in the analysis of potential predictive factors. A Cox regression model allowing for time-dependent covariates will be fitted to identify which factors are predictive of developing HZ. The model will include time to HZ as the outcome variable, the demographic variables age and gender and the *SF-36* variables and *EQ-5D* variables as potential predictors.

Each EQ-5D and SF-36 assessment at a scheduled time point will be re-classified into time points based on the date of assessment relative to date of vaccination:

Studyday=date of assessment – date of vaccination.

The study day will be time component used in the model.

Since there are a maximum of four SF-36 and EQ-5D assessment times we define the variables T_0 , T_1 , T_2 , T_3 as the study day relative to vaccination (day 0) of the QoL assessment and QoL₀ QoL₁, QoL₂, QoL₃ as the values of the QoL assessment at each timepoint. The value of the time-dependent variable QoLt is equal to QoL₀ if $0 < t \le T_1$, QoL₁ if $T_1 < t \le T_2$, QoL₂ if $T_2 < t \le T_3$, with QoLt = QoL₃ if $t > T_3$.

The above model is implemented in SAS as follows:

```
ODS output ParameterEstimates=PE1;

PROC PHREG DATA=tsurv;

CLASS study gender;

MODEL fu_time*hz_conf(0) = age study gender PFT;

PFT=PF0;

IF fu_time > time1 and time1 ne . then PFT=PF1;

IF fu_time > time2 and time2 ne . then PFT=PF2;

IF fu_time > time3 and time3 ne . then PFT=PF3;

RUN;
```

Spearman correlations coefficients will be presented to display the relationships between pairs of variables. In addition, for the quality of life variables, the variance inflation factor and the condition indices for testing multicollinearity will be estimated.

Example: To illustrate the method the following hypothetical 3 subjects are examined:

Table 5 Data from hypothetical subjects to illustrate time dependent covariates

Subject	QoL0	T0	QoL1	T1	QoL2	T2	QoL3	Т3	Censored /day	Event/ day
PPD	80	0	75	425	65	790	24	1050	Yes/1090	No
	90	0	65	420	50	800	45	1050	No	Yes/480
	98	0	43	435	45	790	45	1060	No	Yes/900

204878 (ZOSTER-064)

Statistical Analysis Plan Amendment 1

Table 6 Resolution of hypothetical subject

Subject PPD	Event	Time Interval	QoL
PPD	0	(0, 425]	80
	0	(425, 790]	75
	0	(790, 1050]	65
	0	(1050, 1090]	24

Subject will be censored at day 1090.

Table 7 Resolution of hypothetical subject

Subject	Event	Time Interval	QoL
PPD	0	(0, 420]	90

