	1	(420, 480]	65

Subject had the HZ episode on day 480. The QoL assessment on day 420 is considered as leading to the HZ episode. The subsequent QoL assessments will not be included in the analysis.

Table 8 Resolution of hypothetical subject

Subject	Event	Time Interval	QoL
PPD	0	(0, 435]	98
	0	(435, 790]	43
	1	(790, 900]	45

Subject had the HZ episode on day 900. The QoL assessment on day 790 is considered as leading to the HZ episode. The subsequent QoL assessment at day 1060 will not be included in the analysis.

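### The SAP's model for predictors of HZ leaves out the clinical characteristics and the variable-selection bootstrap planned in the protocol, and SAP section 9 lists neither change

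*SAP*

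**What the plan says.** **Candidate predictors.** Protocol section 10.7.6.3 plans a Cox model in the placebo group and gives, "as potential predictors: demographic and clinical characteristics", followed by the SF-36 and EQ-5D variables. The same section classes characteristics and QoL scores together when it defines what leads to HZ: "Characteristics and QoL scores reported for this subject at the last timepoint before onset of HZ will be considered" as leading to it. The synopsis rationale asks whether "quality of life data and subject characteristics reported by the subjects before the onset of HZ would be predictive of HZ".

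The SAP's list in section 6.3.4 is shorter: "The model will include time to HZ as the outcome variable, the demographic variables age and gender and the time dependent" SF-36 and EQ-5D variables, with adjustment for the original study. Section 7.4 repeats it. The example code is "MODEL fu_time*hz_conf(0) = age study gender PFT", where PFT is one time-dependent QoL scale.

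**Bootstrap.** Protocol section 10.7 states, for the final multivariate model: "A bootstrap analysis will be carried out to evaluate the robustness of the results with respect to the selection of variables". The SAP keeps the P<0.05 screen and the backward elimination. Of the accompanying diagnostics it keeps the Spearman correlations, and says that "the variance inflation factor and the condition indices for testing multicollinearity will be estimated". The supplied SAP text does not mention a bootstrap.

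**Study term.** Protocol section 10.7.6.3 stratifies by trial. SAP sections 6.3.4 and 7.4 use study as a covariate.

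**Declared changes.** SAP section 9 lists four items: QoL timepoints, cohort definitions, the description of serious adverse events and potential immune-mediated diseases, and the placement of QoL tables.

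**The concern.** The objective is to identify factors that predict HZ. If only age, gender and questionnaire variables are offered to the model, a clinical characteristic cannot emerge as a predictor. Nor can the model separate a QoL scale that carries its own information from one that stands in for an illness. Protocol section 1.1.1 itself describes immunosuppressive conditions as consistently related to HZ.

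The bootstrap matters for a different reason. Screening at P<0.05 followed by backward elimination, among scales that may be correlated and with no multiplicity adjustment, can select different predictors in different samples. The bootstrap was the planned means of showing how far the selected set could be trusted.

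Because section 9 is silent on both, a reader of the two documents cannot tell an oversight from a decision.

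**Working it through.** The documents give no figure for this point, so there is none to reproduce. The main check is a comparison of texts. Two illustrative calculations follow.

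**1. Text comparison**

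| Element | Protocol | SAP text | SAP section 9 |
|---|---|---|---|
| Clinical characteristics as candidates | Yes (10.7.6.3) | No (6.3.4, 7.4) | Not listed |
| Bootstrap of variable selection | Yes (10.7) | No | Not listed |
| Trial | Stratum (10.7.6.3) | Covariate (6.3.4, 7.4) | Not listed |
| Spearman, variance inflation, condition indices | Yes (10.7, 10.7.6.3) | Yes (7.4) | No change |

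Three readings that might have closed the gap do not:

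- SAP 6.3.4 says that all factors are first examined in the minimally adjusted model. The only factors it has listed are age, gender, SF-36 and EQ-5D, and only SF-36 and EQ-5D estimates are to be reported from that step. The worked examples in 7.4 likewise carry only QoL forward; one reads "The QoL assessment on day 420 is considered as leading to the HZ episode".
- The bootstrap sentence stands in the general methods section, but the predictor analysis is the only one with a final multivariate model, so the sentence must refer to it.
- The November 2018 SAP has the same two gaps, so SAP Amendment 1 did not introduce them.

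**2. What an omitted condition could do (all inputs assumed)**

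Inputs: condition prevalence p = 0.10; hazard ratio for HZ H = 2; QoL scale with overall SD 1, lower by d = 0.5 or 1 SD in those with the condition, and with no effect of its own; D = 250 confirmed events in the placebo group; HZ treated as a rare event.

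- Prevalence among cases = pH/(1 − p + pH) = 0.20/1.10 = 0.182.
- Shift in the mean scale among cases = d × (0.182 − 0.10) = 0.041 for d = 0.5 and 0.082 for d = 1.
- With SD 1, the log hazard ratio per SD that reproduces this shift is almost the shift itself: 0.0409 and 0.0816 when solved exactly. The apparent hazard ratios per SD lower are exp(0.0409) = 1.042 and exp(0.0816) = 1.085.
- Mean Wald z = log hazard ratio × √D = 0.0409 × 15.81 = 0.65 and 0.0816 × 15.81 = 1.29.
- Chance that |z| > 1.96: 0.099 and 0.252, against 0.05 with no omitted condition.

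**3. What adding candidates costs**

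Inputs: 10 QoL candidates (eight SF-36 scales, EQ-5D utility and EQ-5D visual analogue scale, the ten components of SAP 6.3.1). As an assumption, 13 clinical ones are added: the 12 medical-history categories of SAP Table 4 and one immune-status term. All are null and screened at two-sided 0.05.

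- Independent candidates: 1 − 0.95^10 = 0.40 and 1 − 0.95^23 = 0.69 for at least one entry.
- QoL scales correlated 0.4 or 0.6 (simulation, 400,000 draws): 0.32 or 0.25 with the 10 alone.
- With 13 independent additions, those become 0.65 or 0.61. With additions correlated 0.2 with each other and with the scales, 0.61 or 0.58.

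The chance of at least one null entry therefore rises from 25–40% to 58–69%.

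**The case against.** The case on the other side has real force.

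- **No rule is broken.** Protocol section 10.9 asks for deviations to be described and justified in the final study report, and section 10.7.6.3 leaves further details to the SAP. A reader might infer a breach from the silence of section 9; the documents do not support that. Leaving detail to the SAP does not, however, explain the absence of two named elements, and section 9 was used for something as small as table placement.
- **The analysis is exploratory.** Protocol 10.7 says so, and 10.8 urges caution. This is one secondary objective, and no primary or efficacy result depends on it. That limits the weight of the point. But the section that calls the analysis exploratory is also the one that promises the bootstrap.
- **The protocol never defines clinical characteristics.** This stands. Any particular list is a proposal. It is tempting to say that immune status was promised for this model, but protocol section 8.3.2.1 says only that such data will be used in the analysis, without naming the Cox model. The link is an inference.
- **The bootstrap would not alter the selected model.** This stands too. A reader might infer that leaving it out makes wrong selections more frequent. It does not: selection errors are equally frequent with or without it. What is lost is information about stability.
- **A scale that marks illness is still predictive.** True for prediction alone. But the protocol offered both kinds of candidate to the model, and the objective speaks of identifying factors.
- **Frailty.** A reader might count its absence from the model as a third undeclared change. The rationale names it as a potential risk factor, but the protocol's candidate list for this model does not.
- **Unseen material.** The annex of tables and figures is not available and might include a bootstrap table. The method would still belong in the SAP.

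**Conclusion.** The point holds as two undeclared departures from the protocol in the analysis of one secondary objective. The bootstrap is the clearer one, because it is an explicit commitment. The clinical characteristics are explicitly named but undefined. The move of study from stratum to covariate is a third unlisted change; the documents give no basis for judging its effect.

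This should be corrected before analysis. It does not threaten the primary objective or the efficacy results.

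The size cannot be derived from the documents. In the illustration, an omitted condition gives a scale with no effect of its own an apparent hazard ratio of 1.04 to 1.09 per SD and a 10% to 25% chance of passing the screen instead of 5%. This rests wholly on the assumed 10% prevalence, hazard ratio of 2, difference of 0.5 to 1 SD and 250 events.

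**What to change.** In SAP sections 6.3.4 and 7.4:

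1. Reinstate the bootstrap, applied to the whole procedure (P<0.05 screen and backward elimination), and report how often each variable in the final model is selected.
2. Restore clinical characteristics as candidates, with the set defined by the sponsor before analysis, and report their minimally adjusted estimates alongside those of the QoL scales. The 12 medical-history categories already derived for the frailty index (SAP section 7.3) are one ready source. Immune status, which protocol section 8.3.2.1 says is retrieved centrally, is a possible second one, by inference only.
3. If either element is left out on purpose, record that with the reason in section 9. Record the change of study from stratum to covariate there as well.

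The cost is SAP wording and programming on data the sponsor already holds, plus coding of onset dates if immune status is used as a time-dependent term. The statistical price is more chance entries: with 23 candidates instead of 10, the chance of at least one null entry is 58–69% instead of 25–40%. Bootstrap inclusion frequencies help to flag such entries but do not remove them, which is a reason to keep the clinical set short and to make changes 1 and 2 together.

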1. INTRODUCTION

1.1. Background

Varicella-Zoster Virus (VZV) causes two distinct diseases. Varicella (chickenpox) shortly occurs after primary VZV infection and is characterised by systemic illness and a widely disseminated rash. Herpes Zoster (HZ, shingles) occurs when VZV reactivates from latency and typically manifests as a localised, dermatomal rash. The typical HZ rash usually lasts 2 to 4 weeks and is usually accompanied by pain; that is often described as burning, shooting, or stabbing, and pruritus, which can also be severe, may be as common as pain. In some patients, even touching the affected area lightly may cause severe pain, a phenomenon known as allodynia. The most common complication of HZ is postherpetic neuralgia (PHN), defined as pain that persists after the resolution of the HZ rash. Patients affected by PHN typically report constant burning, throbbing, intermittent sharp or electric shock-like pain, or allodynia. PHN tends to improve over a period of months and about 70-80% of cases resolve within 1 year. However, in some persons PHN persists for many years [Dworkin, 2007].

Inclusion of subjects in clinical trials may be biased for various reasons, e.g. inclusion/exclusion criteria, selection of patients by investigators, self-selection of patients. As such, the aim of this study is to explore if the subjects in the ZOSTER-006 and ZOSTER-022 studies were representative of an older adult population. This will be done by exploring the baseline frailty status and quality of life scores of subjects within the studies.

Several studies have demonstrated that the incidence and severity of HZ increases with age [CDC, 2008]. It is also likely that the incidence and severity of HZ is higher in frail subjects. However, as with age vaccine efficacy may somewhat lower in frail subjects. This study will therefore allow a synthesis of the benefit of vaccination in frail subjects, i.e. in terms of increased incidence, vaccine efficacy, safety and immunogenicity.

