1.2. Rationale for the study

In the course of ZOSTER-006 and ZOSTER-022, Quality of Life questionnaires (QoL), *EQ-5D* and *SF-36*, were completed by all study subjects at baseline. Extracting some elements of these questionnaires and combining them with other medical history data allows attributing of frailty scores.

As these questionnaires were encoded into the respective trial databases only for subjects who developed a suspected Herpes Zoster (HZ) episode during the studies, as per the original study protocols, the purpose of ZOSTER-064 is to allow for the encoding of remaining questionnaires of the subjects and analysis of all questionnaires together. This will allow classification in different levels of frailty and therefore will allow baseline frailty assessment of subjects that took part in the ZOSTER-006 and ZOSTER-022 studies. This will inform the representativeness of the study sample to the general population in older adults, i.e. in terms of the proportion of subjects who are pre-frail and frail. In addition, a comparison of the *SF-36* and *EQ-5D* scores in subjects at baseline

with normative values for those questionnaires in the general population of the countries participating in the study (where these values are available) will also provide further insight in the study population and allow to better understand the study population compared to the overall target population for the vaccine.

Analyses pertaining to efficacy, safety and immunogenicity as per frailty score might then also be performed according to the methodology used in the ZOSTER-006 and ZOSTER-022 studies.

Additionally, the data collected can be used to assess if some physical, physiological and/or psychological characteristics reported by the subjects before the onset of HZ would be predictive of HZ. This will help understand the previously hypothesized predictive factors such as stress or functional status, and also to assess other potential risk factors such as frailty, fatigue or emotional and mental health.

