3. OBJECTIVES

3.1. Primary objective

To assess the baseline frailty of subjects enrolled in ZOSTER-006 and ZOSTER-022.

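### The rationale names frailty as a risk factor for HZ to be assessed, but the SAP's predictor analysis has no frailty term and no age-adjusted frail versus non-frail comparison is specified

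*SAP*

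**What the plan says.** Protocol 1.2 says the data can be used to look for characteristics that predict HZ, "and also to assess other potential risk factors such as frailty, fatigue or emotional and mental health". The synopsis rationale says the same. Protocol 1.1 adds an expectation: "It is also likely that the incidence and severity of HZ is higher in frail subjects".

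For the predictor analysis in the placebo group, protocol 10.7.6.3 says: "The model will include time to HZ as the outcome variable and as potential predictors: demographic and clinical characteristics", followed by the SF-36 and EQ-5D variables. It does not define clinical characteristics. Protocol 8.3.2.1 notes that medical history and immune-compromising conditions or treatments will be retrieved centrally for the analysis.

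SAP Amendment 1, section 6.3.4, is narrower: "The model will include time to HZ as the outcome variable, the demographic variables age and gender and the time dependent" SF-36 and EQ-5D variables, with further adjustment for original study. Section 7.4 repeats the list. Its example code has the covariates "age study gender PFT", the last being one time-dependent SF-36 scale. The planned output is also limited: "The parameter estimates and standard error of each SF-36 and EQ-5D parameter from the minimally adjusted model will be presented", plus the final multivariate model.

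SAP Section 9 lists four changes from the protocol: questionnaire timepoints, cohort definitions, description of serious and immune-mediated events, and placement of tables. The shorter predictor list is not among them.

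**The concern.** The study exists to derive a frailty index and classify subjects by it. Its rationale names frailty, fatigue, and emotional and mental health as risk factors to be assessed. Fatigue has the Vitality scale, and emotional and mental health have Role Emotional and Mental Health, so each has a term in the SAP's models. Frailty has none.

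Run as written, the analysis of predictive factors will report single questionnaire scores adjusted for age, gender and study, and nothing for the composite. What remains on frailty and HZ is cases and follow-up by frailty category, from which a reader can form an incidence. Protocol 1.1.1 treats age as the most common risk factor for HZ. An incidence contrast without age adjustment therefore cannot separate frailty from age if frail subjects are older.

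**Working it through.** **1. The plan's own item count.** From SAP 7.3, Table 3: SF-36 Q1 (1) + Q11 (4) + Q3 (10) + Q9 (9) + Q2 (1) + four EQ-5D items (4) = 29. Adding 12 medical history categories gives 41. Both totals reproduce.

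**2. How much of the index reaches a predictor model.** Take the SF-36 variables to be the eight scales of protocol 10.7.2, Table 2. The items for Q1, Q11, Q3 and Q9 feed those scales (24 items), and the four EQ-5D items feed the EQ-5D score, so 28 items enter, split across separate scores. Q2 (health transition) is scored in no scale, and medical history is not a predictor: 1 + 12 = 13 items, or 13/41 = 32%, enter no model. The composite does not enter either.

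**3. Whether another analysis fills the gap.**
- Vaccine efficacy by frailty (SAP 6.3.2) is estimated separately in each category. The contrast is vaccine against placebo, not frail against non-frail.
- Burden of illness (SAP 6.3.3) tabulates confirmed cases and total follow-up by frailty category and arm in the mTVC. Placebo incidence by category follows, with no age adjustment stated.
- Frailty by age group (SAP 6.2.1) and age by frailty status (SAP 6.1) describe any imbalance but do not link it to HZ.

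**4. What age mix alone could produce.** Protocol 1.1.1 gives about 5 cases per 1000 per year at 50-59 and 10 at 60 and over. With share s aged 60 or over, the rate is 5(1 - s) + 10s. The shares below are assumptions, with no frailty effect built in.

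| Aged 60+, frail v non-frail | Rates per 1000 | Ratio |
|---|---|---|
| 95% v 80% | 9.75 v 9.0 | 1.08 |
| 90% v 75% | 9.5 v 8.75 | 1.09 |
| 90% v 60% | 9.5 v 8.0 | 1.19 |
| 95% v 60% | 9.75 v 8.0 | 1.22 |
| 100% v 50% | 10.0 v 7.5 | 1.33 |

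The last row is an extreme, since all ZOSTER-022 subjects were 70 or older.

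**5. Whether a frailty term is estimable.** SAP 6.3.6.2 expects about 5% frail. The documents give no confirmed placebo event count, only about 1000 suspected cases over both arms (protocol 10.4). Assume E placebo events, 45% non-frail, and event shares equal to subject shares. Then SE(log HR, frail v non-frail) = sqrt(1/(0.05E) + 1/(0.45E)).
- E = 400 (20 frail events): sqrt(1/20 + 1/180) = 0.236, so 95% limits are the HR times or divided by exp(1.96 × 0.236) = 1.59.
- E = 800 (40 frail events): sqrt(1/40 + 1/360) = 0.167, factor 1.39.

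For frail against all others, the HR detectable with 80% power is exp((1.960 + 0.842)/sqrt(E × 0.05 × 0.95)). This is 2.10, 1.78, 1.63 and 1.53 for 300, 500, 700 and 900 events. Power at HR 1.5 is 33%, 51%, 65% and 76%. Correlation between frailty and age would worsen all of these figures.

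**The case against.** The case against is that this is an exploratory study whose primary objective, "To assess the baseline frailty of subjects enrolled in ZOSTER-006 and ZOSTER-022", is descriptive. No listed objective asks whether frail people develop more HZ, and the rationale is worded softly. Most index items are already examined, adjusted for age, through the questionnaire scores. All of that is fair. It limits the weight of the point, but it does not explain why one named factor has no term when the others do.

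A reader might go further in four ways that the documents do not support.
- *That the protocol also leaves frailty out.* Its clinical characteristics are undefined and could cover frailty status or medical history. The explicit omission is in the SAP.
- *That the benefit synthesis in protocol 1.1 needs age adjustment.* Absolute benefit in frail people depends on their incidence as they are, age included, which the burden-of-illness table can supply. Age adjustment is needed for the risk-factor question in protocol 1.2.
- *That efficacy by frailty is unadjusted.* SAP 6.3.2 and 7.1.2 refer to the parent-study SAPs for that model, and those are not available here.
- *That a misleading frailty effect will be reported.* The plan shows frailty by age, so a careful reader can see an imbalance. The documents do not give its size.

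**Conclusion.** The point stands in this form. A factor that the rationale says will be assessed is absent from the SAP's predictor list, example code and planned output. The protocol's wider predictor class was dropped without being recorded as a change, and no other specified analysis gives an age-adjusted frail versus non-frail comparison. On the eight-scale reading, 32% of the index items and the composite are untested.

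The crude ratio of about 1.1 to 1.3 illustrates what age alone could do. It rests on assumed age mixes and a two-step incidence curve, and is not an estimate of bias in these data. The precision figures rest on assumed event counts and an assumed 45% non-frail. The upper counts are generous beside about 1000 suspected cases in both arms. At those values the confidence limits (a factor of 1.39 to 1.59) are wider than the illustrated age effect, so the added result is an exploratory estimate with limited power for moderate effects. No primary or efficacy result is at risk. The change should be made because it answers a stated question with variables already derived.

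**What to change.** In SAP 6.3.4, add for the placebo group of the TVC:
- a prespecified Cox model for time to confirmed HZ with baseline frailty status (pre-frail and frail v non-frail), adjusted for age, gender and original study;
- a second model with the frailty index per 0.1 and the same adjustment;
- hazard ratios with 95% CIs, labelled exploratory;
- exclusion of subjects with unknown frailty status (under SAP 7.3, those with more than 10 missing questionnaire components), with their number and HZ cases reported;
- a statement that these models stay separate from the multivariate SF-36/EQ-5D model, because the index is built largely from the same items;
- a statement that precision is limited, given about 5% frail, an unstated number of placebo events and likely correlation with age.

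In SAP Section 9, record that the protocol's clinical characteristics were dropped as predictors, with the reason. If the sponsor prefers not to fit the models, frailty should come out of the rationale's list of risk factors and that change should be recorded too.

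The cost is a paragraph of SAP text, an entry in Section 9 and two further PHREG calls. No new data are needed.
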